6.8 Investigational Medicinal Product Accountability

The Investigator or suitably qualified designee is responsible for ensuring IMP, inoculum, and rescue medications accountability, including reconciliation of drugs and maintenance of records.

- Upon receipt of the IMP/inoculum/rescue medications, the responsible person will check for accurate delivery and acknowledge receipt by signing or initialing and dating the appropriate documentation and returning it to the location specified. A copy will be archived for the Investigator Site File

- IMP/inoculum/rescue medications dispensing will be recorded on the appropriate drug accountability forms so that accurate records will be available for verification at each monitoring visit
- Trial site IMP/inoculum/rescue medications accountability records will include the following
 - Confirmation of IMP/inoculum/rescue medications receipt, in good condition and in the defined temperature range
 - The inventory of IMP/inoculum/rescue medications provided for the clinical trial and prepared at the site
 - The use of each dose by each subject
 - The disposition (including return, if applicable) of any unused IMP/inoculum/rescue medications
 - Dates, quantities, batch numbers, vial numbers, expiry dates, formulation (for IMP/inoculum/rescue medications prepared at the site), and the individual subject trial numbers.

The Investigator site should maintain records, which adequately document that subjects were provided the doses specified in this protocol, and all IMP/inoculum/rescue medications provided were fully reconciled.

Unused IMP/inoculum/rescue medications must not be discarded and/or used for any purpose other than the present trial. No IMP/inoculum/rescue medications that is dispensed to a subject may be redispensed to a different subject.

A Trial Monitor will periodically collect the IMP/inoculum/rescue medications accountability forms.

6.9 Assessment of Investigational Medicinal Product Compliance

The IMP will be administered by the trial site personnel within the confines of the trial site. A mouth and hand check will be performed after each dose administration to ensure that all doses have been swallowed.

6.10 Blinding

The trial will be double-blind in Part A and Part B. Part C will be open-label. Blinding will be maintained throughout the duration of the relevant trial part, ie, until the database lock of Part A and until the database lock of Part B. The randomization list is to be kept strictly confidential, accessible only to authorized persons (eg, randomization statistician, pharmacists, and the bioanalytical laboratories that prepare and analyze relevant samples), until the time of unblinding. Interim PK analyses will be performed blinded (ie, utilizing dummy subject numbers which cannot be linked to the subject identifiers used in the trial site). In addition, data listings (ie, utilizing dummy subject numbers different from those used for the PK analysis) will be provided in a blinded manner to support dose escalation or dose modification decisions by the SMC. After each cohort in Part A and Part B, the SMC will review data on safety and tolerability. Their ensuing

decision will generally be made without breaking the randomization code. If judged necessary by the SMC, an individual subject or the complete cohort may be unblinded during evaluation of the trial data. Before unblinding, the SMC should document the decision to unblind and any planned action to be taken based on the revealed treatment allocation.

Only when the trial (all 3 parts) is completed, database locked, the data file verified, and protocol deviations determined, will the drug codes be broken and made available for data analysis. However, if the Sponsor decides to lock the database corresponding to a trial part (ie, Part A, or Part B, or Part C) for the purpose of a final analysis of that trial part, then that trial part may be unblinded after the data file is verified and protocol deviations determined. Furthermore, if the Sponsor considers it necessary for timely decision-making, a trial-independent statistician/modeler may be directed to receive the randomization code for a trial part after the trial is completed, but prior to database lock, for that trial part. All breaks of the trial blind must be adequately documented.

6.11 Emergency Unblinding

Part A and Part B only

The trial blind may be broken for an individual subject only if knowledge of the IMP is essential for clinical management of the subject. The Investigator or designee will unblind the subject using the individual code-break envelope provided by the randomization statistician. The Investigator must promptly explain the reason for any unblinding of an IMP to the Sponsor without revealing the result to any Sponsor employee except the designated Drug Safety representative (using the Emergency Unblinding Notification Form).

The Investigator must record the date of unblinding and the reason in the eCRF. Contact information for breaking the blind in an emergency is given on the subject emergency card provided to each subject. Under certain circumstances, Drug Safety may be required to unblind the treatment assignment for an individual subject following an SAE or other serious event; for example, if an expedited regulatory report is required.

Once the treatment code has been broken for a subject, administration of IMPs will be stopped and the subject will be withdrawn from the trial. The subject will attend the Early Termination visit.

6.12 Treatment of Overdose

An overdose is defined as any dose greater than the highest daily dose included in a clinical trial protocol or planned for an individual subject enrolled in the trial. Even if it does not meet other criteria for an SAE, any overdose must be recorded in the trial medication section of the eCRF and reported to Drug Safety in an expedited manner using the SAE Report Form, and following the procedure in Section 7.4.

The effects of an M5717 overdose are unknown, and therefore no standard treatment is currently established. In the event of an overdose, the Investigator or treating physician should use appropriate clinical judgment for the evaluation and management of any clinical signs, symptoms, and laboratory results.

Refer to the package inserts of the rescue medication in [Appendix VII](#) for details regarding the effects and management of an overdose.

6.13 Medical Care of Subjects after End of Trial

In this trial in healthy subjects, no further treatment or medical care is planned or required after the end of the trial.

7 Trial Procedures and Assessments

Prior to performing any trial assessments, the Investigator will ensure that the subject has provided written informed consent according to the procedure described in [Section 9.2](#).

A subject identifier (see [Section 6.3](#)) will be assigned for each subject for whom written informed consent has been obtained.

All efforts should be made to perform assessments as close as possible to the scheduled time points.

Compliance to protocol specific requirements will be checked at each visit and subjects are given reminders each time they leave the trial site.

At visits where assessment time points coincide with each other, the following procedure should be followed: perform vital signs assessments slightly before the specific time point, ECG assessments on time, PK blood sampling directly following ECG.

Samples and assessments obtained within the defined window (see [Table 4](#)) from dosing will not be captured as a protocol deviation, as long as the exact time of the assessment/sample collection is noted on the source document and data collection tool (eg, eCRF).

7.1 Schedule of Assessments

The Schedule of Assessments for Part A, Part B, and Part C is provided in [Table 1](#) to [Table 3](#).

7.1.1 Screening Examinations

All subjects will undergo an entry examination to evaluate their health status. This examination will be conducted not more than 28 days prior to the planned first IMP or inoculum administration. Only subjects who meet the inclusion criteria and none of the exclusion criteria will be enrolled in the trial.

Prior to any Screening examinations the subjects have to sign the Participant Information Consent Form (PICF). The assessments to be performed at Screening are indicated in the Schedule of Assessments ([Table 1](#) to [Table 3](#)). Safety laboratory assessments with results outside of the normal laboratory range may be repeated once.

Subjects who fail to meet the protocol specified inclusion- or exclusion criteria, or who withdraw their consent in the Screening period are considered screening failures. The following data, as a

minimum, should be recorded for these subjects: date of informed consent, inclusion/exclusion criteria, demographics (including age, sex (gender), weight, and height), AEs (if any) from the date of informed consent until the subject is considered a screen failure by the Investigator, reason for screening failure, and the Investigator's signature.

7.1.2 Treatment Periods

A review and update of the subject's inclusion/exclusion criteria to ensure the subject remains eligible for participation in the trial should be performed prior to admission to the trial site. Eligible subjects will be randomized to active treatment or placebo in Part A and Part B, or enrolled to the challenge and active treatment in Part C. Subjects will be admitted to the trial site on Day -2 for Part A and Part B, and Day 1 for Part C. Subjects will be discharged after completion of the required assessments on Day 7 for Part A and Part B, and between Day 4 to Day 7, at the discretion of the Investigator on advice of the SMC.

The assessments to be performed at specific time points are indicated in the Schedule of Assessments (Table 1 to Table 3).

7.1.3 Ambulant Visits

Ambulant visits will be performed at regular intervals from Day 8 onwards for Part A and Part B. In Part C, ambulant visits will be performed on Inoculum Days prior to IMP administration and at regular intervals from Day 4 onwards. In Part C, an ambulant visit will be performed on Day 22 for subjects with breakthrough infections for the administration of rescue medication.

In addition, subjects will be regularly contacted (approximately every 2 to 3 days) by telephone during their ambulant period.

The assessments to be performed at specific time points are indicated in the Schedule of Assessments (Table 1 to Table 3).

7.1.4 Follow-up Visits

Subjects will be asked to return to the trial site for Follow-up visits on Day 13, Day 15, Day 17 (Part A and Part C), Day 22, Day 29 (Part C only), Day 33, and Day 44 for Part A, Part B, and Part C. The assessments to be performed at these time points are indicated in the Schedule of Assessments (Table 1 to Table 3).

7.1.5 Phone Calls

On Day 8 and Day 10 of Part A and Part B, subjects may be contacted by the trial site via a phone call or subjects may text a photo of their completed diary card instead of visiting the trial site. In Part C, the subject will be contacted daily via phone calls while outpatient, from Inoculum Day 2 to Inoculum Day 4, as well as on Day 23 to Day 25, for a safety check and compliance of rescue medication use.

7.1.6 End of Trial/Early Termination Visit

The End of Trial examination has to verify that all values tested in the Screening have remained within a clinically acceptable range. The relevant tests will be performed on Day 44 (± 2 days) for Part A, Part B, and Part C. The assessments to be performed at these time points are indicated in the Schedule of Assessments (Table 1 to Table 3).

Unacceptable values and AEs will be followed up until they return to baseline/resolved or there is an adequate explanation which is not related to the trial.

7.2 Demographic and Other Baseline Characteristics

At Screening, the following demographic data will be collected: date of birth, sex (gender), race, and ethnicity.

Furthermore, the following will be documented:

- Height, weight, and BMI
- Skin type according to the Fitzpatrick scale (Appendix VI)
- Clinically relevant findings in the medical history are recorded
- Prior medications within 4 weeks (any medication with enzyme inducing or inhibiting properties) or 2 weeks (any prescribed medicine or over-the-counter drug [other than occasional ibuprofen < 1 g or paracetamol < 1 g] or dietary supplement including herbal remedies, vitamins, and minerals)
- Smoking status, alcohol intake
- Female status (WNCBP, postmenopausal, sterilization).

7.3 Efficacy Assessments

Clinical endpoints: Part A and B; not applicable.

Clinical endpoints: Part C; Parasitological effect of M5717, defined as the reduction and/or clearance of parasitemia by qPCR up to Day 8, (see Section 5.2.4).

The malaria clinical score is defined in Appendix IV and needs to be assessed in case any malaria-related symptoms are seen.

Surrogate endpoints: Not applicable.

Follow-up: Not applicable.

Efficacy examinations will be scheduled according to the applicable Schedule of Assessments (Table 3).

7.4 Assessment of Safety

The safety profile of the IMP will be assessed through the recording, reporting and analysis of baseline medical conditions, AEs, physical examination findings including vital signs, 12-lead ECGs, and safety laboratory tests.

Comprehensive assessment of any apparent toxicity experienced by each subject will be performed from the time of giving informed consent and throughout the trial. The Investigator will report any AEs, whether observed by the Investigator or reported by the subject (see Section 7.4.1.2). The reporting period for AEs is described in Section 7.4.1.3. The expected signs and symptoms of malaria after administration of the inoculum in Part C is detailed in Appendix V.

7.4.1 Adverse Events

7.4.1.1 Adverse Event Definitions

Adverse Event

An AE is any untoward medical occurrence in a subject or clinical investigation subject administered a pharmaceutical product, regardless of causal relationship with this treatment. An AE can therefore be any unfavorable and unintended sign (including an abnormal laboratory finding), symptom, or disease temporally associated with the use of a medicinal product, whether or not considered related to the medicinal product.

For surgical or diagnostic procedures, the condition/illness leading to such a procedure is considered as the AE rather than the procedure itself.

The Investigator must assess the severity of AEs according to the QTS as described in the “Toxicity Grading Scale for Healthy Adult and Adolescent Volunteers Enrolled in Preventive Vaccine Clinical Trials”, as follows:

Mild (Grade 1): The subject is aware of the event or symptom, but the event or symptom is easily tolerated.

Moderate (Grade 2): The subject experiences sufficient discomfort to interfere with or reduce his or her usual level of activity.

Severe (Grade 3): Significant impairment of functioning: the subject is unable to carry out his or her usual activities.

Potentially Life-Threatening (Grade 4): Extreme limitation to daily activity. Significant assistance required. Significant medical intervention, hospital or hospice care very likely.

Investigators must also systematically assess the causal relationship of AEs to the IMP or inoculum using the following definitions. Decisive factors for the assessment of causal relationship of an AE to the IMP include, but may not be limited to, temporal relationship between the AE and the IMP,

known (from animal studies) side effects of the IMP, known side effects of the inoculum, medical history, concomitant medication, course of the underlying disease, trial procedures.

Unrelated: Not reasonably related to the IMP or inoculum or rescue medication. AE could not medically (pharmacologically/clinically) be attributed to the IMP/inoculum/rescue medication under investigation in this clinical trial protocol. A reasonable alternative explanation must be available.

Related: Suspected to be reasonably related to the IMP or inoculum or rescue medication. AE could medically (pharmacologically/clinically) be attributed to the IMP/inoculum/rescue medication under investigation in this clinical trial protocol.

The outcome should be entered with terms described below:

- Recovered without sequelae
- Recovered with sequelae
- Ongoing
- Fatal
- Unknown.

In case of a fatality, the cause of death is considered as the SAE, and the death is considered as its OUTCOME.

Abnormal Laboratory Findings and Other Abnormal Investigational Findings

Abnormal laboratory findings and other abnormal investigational findings should not be reported as AEs unless they are associated with clinical signs and symptoms, lead to treatment discontinuation or are considered otherwise medically important by the Investigator. If a laboratory abnormality fulfills these criteria, the identified medical condition must be reported as the AE rather than the abnormal value itself.

Serious Adverse Events

An SAE is any untoward medical occurrence that at any dose:

- Results in death
- Is life-threatening. (Note: The term “life-threatening” refers to an event in which the subject is at risk of death at the time of the event, not an event that hypothetically might have caused death if it was more severe)
- Requires inpatient hospitalization or prolongs an existing hospitalization
- Results in persistent or significant disability or incapacity
- Is a congenital anomaly or birth defect

- Is otherwise considered to be medically important. (Note: Important medical events that may not result in death, be life-threatening, or require hospitalization may be considered as SAEs when, based upon appropriate medical judgment, they may jeopardize the subject or may require medical or surgical intervention to prevent one of the outcomes listed above. Examples of such events include allergic bronchospasm requiring intensive treatment in an emergency room or at home, blood dyscrasias or convulsions that do not result in inpatient hospitalization, or the development of drug dependency or drug abuse).

For the purposes of reporting, any suspected transmission of an infectious agent via an IMP/inoculum is also considered an SAE and should be reported in an expedited manner, as described in Section 7.4.1.4.

Events that Do Not Meet the Definition of an SAE

Elective hospitalizations to simplify trial treatment or trial procedures (for example, an overnight stay to monitor initiation of treatment with the IMP is not considered an SAE. However, all events leading to unplanned hospitalizations or unplanned prolongation of an elective hospitalization (for example, undesirable effects of any administered treatment) must be documented and reported as SAEs.

Events Not to Be Considered as AEs/SAEs

Medical conditions present at the initial trial visit that do not worsen in severity or frequency during the trial are defined as Baseline Medical Conditions, and are not to be considered AEs.

Adverse Events of Special Interest

The assessments to be performed for assessment of AESIs is detailed in Section 7.4.4.7.

The following are identified as AESIs in this trial:

- Vomiting or diarrhea
- Liver enzyme elevations (ALT/AST/Bilirubin)
- Cutaneous reactions (local tolerability CRF for severity of redness, swelling, induration, bruising, and itching)
- Photosensitivity/light sensitivity
- Pregnancy in a female partner of a male subject.

AESIs for monitoring should be reported following the procedure for an SAE described in Section 7.4.1.4.

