7.4.1.2 Methods of Recording and Assessing Adverse Events

At each trial visit, the subject will be queried on changes in his or her condition. During the reporting period, any unfavorable changes in the subject's condition will be recorded as AEs, whether reported by the subject or observed by the Investigator.

Complete, accurate, and consistent data on all AEs experienced for the duration of the reporting period (defined below) will be reported on an ongoing basis in the appropriate section of the eCRF. Among these AEs, all SAEs and all nonserious AESIs must be additionally documented and reported using a Serious Adverse Event Report Form as described in Section 7.4.1.4.

It is important that each AE report include a description of the event, its duration (onset and resolution dates [and times, when it is important to assess the time of AE onset relative to the recorded treatment administration time]), its severity (according to the QTS as described in the “Toxicity Grading Scale for Healthy Adult and Adolescent Volunteers Enrolled in Preventive Vaccine Clinical Trials”), its causal relationship with the IMP or rescue medication, any other potential causal factors, any treatment given or other action taken (including dose modification or discontinuation of the IMP), and its outcome. In addition, serious cases should be identified and the appropriate seriousness criteria documented.

Specific guidance can be found in the eCRF Completion and Monitoring Conventions provided by the CRO in coordination with of the Sponsor.

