8.5.2 Analysis of Primary Endpoints

8.5.2.1 Safety

Part A and Part B

Safety data analysis will be conducted on the Safety Analysis Set. The number and percentage of subjects experiencing one or more AEs will be summarized by dose level group, relationship to IMP, and severity. AEs will be coded using Medical Dictionary for Regulatory Activities terminology. Laboratory parameters will be summarized using descriptive statistics, by postdose shifts relative to baseline, and data listings of abnormal results as appropriate. Vital signs and ECG data will be summarized for observed and changes-from-baseline values by dose level using descriptive statistics. Clinically noteworthy ECG findings for individual subjects will be listed and summarized as appropriate.

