#### 15.1.1 All Adverse Events

Treatment-emergent AEs will be summarized by dose and overall in tables with:

 The number and percentage of subjects with any TEAE, any IMP-related TEAE, any serious TEAE, any IMP-related serious TEAE, any Grade ≥3 TEAE, any IMP-related Grade ≥3 TEAE, any AEs of special interest (AESI), any TEAE leading to death, any IMP-related TEAE leading to death, any TEAE leading to study discontinuation

- The number and percentage of subjects with at least one TEAE by SOC and PT
- The number and percentage of subjects with at least one TEAE by worst grade, SOC, and PT
- The number and percentage of subjects with at least one IMP-related TEAE by SOC and PT
- The number and percentage of subjects with at least one TEAE by PT only, sorted in decreasing incidence overall
- The number and percentage of subjects with non-serious TEAEs by SOC and PT
- The number and percentage of subjects with at least one AESI recorded by SOC and PT.

Unless otherwise stated, AEs will be displayed with SOC terms and PTs within each SOC term sorted alphabetically.

For determining incidence counts, within each level of TEAE term, if a subject experiences more than one occurrence, the subject will only be counted once for that TEAE.

If an AE is reported for a given subject more than once during treatment, the worst severity and the worst relationship to study treatment will be tabulated.

Adverse events related to IMP are those events with relationship missing, unknown or yes.

In case a subject had events with missing and non-missing severity, the maximum non-missing severity will be displayed.

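### Part C: as written, post-dose events due only to malaria or rescue medication would be counted as M5717-related, unless the eCRF rates each agent separately

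*Protocol*

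**What the plan says.** **Protocol 7.4.1.1** introduces the assessment as covering two agents: "Investigators must also systematically assess the causal relationship of AEs to the IMP or inoculum using the following definitions". The two categories that follow cover three: "Unrelated: Not reasonably related to the IMP or inoculum or rescue medication" and, for Related, "Suspected to be reasonably related to the IMP or inoculum or rescue medication". The same section lists factors for judging causality to the IMP, and these include "known side effects of the inoculum".

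**Protocol 7.4.1.2** lists what each AE report must contain, including "its causal relationship with the IMP or rescue medication". The inoculum is not mentioned.

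**Protocol 8.5.2.1** has AEs in Parts A and B "summarized by dose level group, relationship to IMP, and severity". Section 8.5.3.2 says Part C safety data are analysed similarly.

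**SAP 15.1.1** plans overview rows for IMP-related TEAEs (any, serious, Grade 3 or higher, leading to death) and a table of IMP-related TEAEs by SOC and PT. Its rule is: "Adverse events related to IMP are those events with relationship missing, unknown or yes". No inoculum-related or rescue-related summary is planned.

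**SAP 15.1** defines TEAEs by onset on or after first dosing. Events that begin before dosing and either resolve before it or do not worsen after it are listed as pre-treatment and stay out of the summary tables unless otherwise stated.

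**The concern.** In Part C every subject is deliberately infected, then dosed with M5717, then given Riamet. There is no placebo group, so the investigator's attribution is one of the few ways to separate drug effects from the disease and from the rescue drug. A category that pools the three agents cannot carry that distinction into the tables.

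The signals overlap. The protocol names vomiting as a malaria symptom (3.1) and transient ALT rises as a possible effect of infection (3.3.3). Vomiting and liver enzyme elevations are also adverse events of special interest for M5717 (7.4.1.1), and 4 of 8 subjects in the 1,000 mg cohort of Part A had liver enzymes above the upper limit of normal (5.2.2).

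Part C safety data are among the inputs to the decision on whether, and at which dose, to go to Phase II (5.2.1). The SMC reviews them when deciding on a further Part C cohort and its dose (5.2.8).

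**Working it through.** The documents give no figure on this point, so there is none to reproduce. The check sets the texts side by side and then gives the scale.

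**Step 1: which agents are assessed?**

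| Place | Agents named |
|---|---|
| Protocol 7.4.1.1, lead-in | IMP, inoculum |
| Protocol 7.4.1.1, both categories | IMP, inoculum, rescue medication (pooled) |
| Protocol 7.4.1.2, AE report content | IMP, rescue medication |
| Protocol 8.5.2.1, summaries | IMP |
| SAP 15.1.1, rule for IMP-related | an unspecified relationship variable |

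No place requires one rating per agent. The SAP's values (missing, unknown, yes) are also not the protocol's two categories, so the source variable is undefined.

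**Step 2: where does each kind of Part C event go?** One pooled field is compared with separate fields.

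| Event, as judged by the investigator | Pooled field | Separate fields |
|---|---|---|
| Malaria symptom before dosing, resolved or not worsened | not tabulated | not tabulated |
| Malaria symptom starting or worsening after dosing, due to inoculum only | IMP-related | not IMP-related |
| Symptom of recrudescence only | IMP-related | not IMP-related |
| Event due to Riamet only | IMP-related | not IMP-related |
| Event due to M5717 | IMP-related | IMP-related |
| Event due to none of the three | not IMP-related | not IMP-related |

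The two arrangements differ in rows 2 to 4. Those rows need not be empty:

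- Subjects are dosed at an expected parasitemia of at least 5,000/mL, and doses leading to recrudescence are part of the design (Synopsis, Part C methodology).
- All subjects receive Riamet (5.2.5).
- AE collection runs to Day 44 ± 2 (7.4.1.3), and the SAP's TEAE definition has no closing date.

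**Step 3: scale.** Inputs are 8 subjects per cohort and up to 3 cohorts, so up to 24 subjects. SAP 15.1.1 counts a subject once per level of term.

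- One subject whose only related TEAE falls in rows 2 to 4 adds 1/8 = 12.5 percentage points to that cohort's IMP-related rate.
- Over all of Part C, the same subject adds 1/24 = 4.2 points.
- The number of such subjects is not given. The possible range per cohort is 0/8 = 0% to 8/8 = 100%.

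**Step 4: which outputs are touched?** Only those that use relationship: the IMP-related overview rows and the IMP-related SOC/PT table. Tables of all TEAEs, of worst grade and of events of special interest do not depend on it.

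**The case against.** The strongest reply is that the recording form has not been seen. Protocol 7.4.1.2 refers to eCRF completion conventions and 10.1 to the Manual of Operations; neither is in the documents. If the form has a field per agent, the SAP can simply use the IMP field. The defined terms support that reading. Protocol 6.1 describes only M5717 and placebo as IMP, 6.4 places the inoculum and rescue drugs under a separate heading, and the SAP safety set names M5717 as the IMP in Part C. The factors in 7.4.1.1 also describe a judgement about the IMP, with inoculum effects weighed in it. This stands as a condition on the conclusion. It does not remove the need for the SAP to name its variable or for 7.4.1.1 and 7.4.1.2 to agree.

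The pre-treatment rule also stands: malaria symptoms before dosing that do not worsen after it are outside the tables. It does nothing for events with onset or worsening after dosing.

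Attribution is not the only safeguard. Part A is placebo-controlled and malaria-free, Part C doses may not exceed the highest dose given in Part A or B, and the malaria clinical score is summarized by dose (SAP 15.2.3). These help interpretation but do not correct a misattributed table entry.

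A reader might infer more: that malaria symptoms are in fact counted as M5717-related, or that lower doses will show worse apparent tolerability because malaria persists or returns. The first depends on the unseen eCRF. The second is possible, but the documents give no event rates by dose to support it.

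**Conclusion.** The concern holds in a conditional form. Under the definitions as written, Part C TEAEs due only to induced malaria, recrudescence or Riamet would be reported as M5717-related. This assumes that relationship is captured in one field using the 7.4.1.1 categories and that the SAP's rule is applied to that field. If the eCRF already rates each agent, the defect reduces to inconsistent wording and an unnamed SAP variable.

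The size is 12.5 percentage points per affected subject in a cohort of 8, with 0 to 8 subjects affected. The documents do not allow a narrower estimate.

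The consequence is limited to descriptive tables for a secondary endpoint, in a trial with no formal hypothesis testing. It would be wrong to infer that dose escalation is affected through the suspension rules: those in Protocol 5.5.3 apply to Parts A and B, where no inoculum is given. SMC analyses are left to its charter (SAP 6.1), so an effect on Part C dose decisions cannot be shown from the documents. The change is still worth making, because Part C is uncontrolled and its safety data inform later planning.

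**What to change.** 1. **Protocol 7.4.1.1 and 7.4.1.2:** name the same agents in both. For each Part C AE, require a separate related/unrelated assessment for M5717, for the inoculum or infection, and for rescue medication. Use existing eCRF fields if they are there.
2. **SAP 15.1.1:** derive IMP-related from the M5717 assessment only, name that variable, and map its values to the protocol's categories. Keep the rule that missing or unknown counts as related, applied to that field only.
3. **SAP 15.1.1, Part C:** add summaries of inoculum-related and rescue-related TEAEs beside the IMP-related ones.

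The cost is up to two extra CRF fields per Part C AE, a small added burden on the investigator, and minor table work. If the fields already exist, only wording and tables change. No subjects or procedures are added.
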